5. STUDY POPULATION

5.1. General

The ITT analysis set will be used for all study population summaries unless otherwise specified. Summaries will be presented for all patients.

5.2. Patient Disposition

Data from patients who are enrolled; patients enrolled but not treated; patients in the ITT; patients who complete the treatment period; patients who withdraw from the treatment period; patients who complete the end of study visit, and patients who withdraw from the study will be summarized using descriptive statistics.

Data from patients who withdraw from the treatment period and withdraw from the study will also be summarized by reason for withdrawal using descriptive statistics.

5.3. Demographics and Baseline Characteristics

Patient demographic and baseline characteristics will be summarized using descriptive statistics.

Body mass index (BMI) will be computed as:

$$\text{BMI (kg/m}^2\text{)} = \text{Weight at baseline (kg)}/[\text{Height at screening (m)}^2]$$

Normal age and sex-based z-scores and percentiles for BMI will be determined using the World Health Organization (WHO) growth charts. Age and sex-based BMI categories includes: Underweight (< 5 percentile), Normal ($\geq 5 - < 85$ percentile), Overweight ($\geq 85 - < 95$ percentile), Obese (≥ 95 percentile).

The continuous variables of patient age, weight, height, BMI, BMI WHO adjusted z-scores and percentile, will be summarized using descriptive statistics.

The categorical variables of patient weight group, sex, race, ethnicity, region (United States (US) and non-US), country for non-US, age group (6 to 11 years, 12 to 18 years), CYP2D6 impairment status (Impaired/Not impaired), and BMI categories will be summarized using descriptive statistics for each category. Missing categories will be presented if necessary.

5.4. Disease Characteristics

Not applicable.

5.5. Medical History

All medical history will be coded using the Medical Dictionary for Regulatory Activities (MedDRA). The incidence of medical history abnormalities will be summarized using descriptive statistics by system organ class (SOC) and preferred term. Patients are counted only once in each preferred term and SOC category. Summaries will be presented for all patients.

5.6. Prior Therapy and Medication

Any prior or concomitant medication a patient has had within 30 days prior to baseline and up to the end of study, including follow up, will be recorded on the case report form (CRF). Generic or trade name, indication, dose, and start and end dates of the administered medication will be recorded. The sponsor will encode all medication according to the WHO drug dictionary.

The incidence of prior therapies and medications will be summarized using descriptive statistics by therapeutic class, preferred base name and preferred term. Patients are counted only once in each therapeutic class category, and only once in each preferred term category. Prior therapies and medications will include all medications taken and therapies administered before the first day of IMP administration.

5.7. Study Drug Titration

The number and percent of patients at each dose level by weight group and CYP2D6 impairment status during the titration period will be summarized by week. The latest administered dose in each study week will be used.

Reasons for the deviation from the IMP administration will be summarized overall and by period (titration and maintenance).

Descriptive statistics of the maintenance dose (last dose taken in the maintenance period; nominal and as percent of the maximal planned dose for the patient) will be presented.

5.8. Study Drug Compliance

Study drug compliance during the treatment period will be assessed at described in the protocol Section 5.7.

Study drug compliance will be determined by presenting the number of tablets taken as a percentage of the expected number of tablets based on the dose(s) of the patient at the relevant time period (see [Table 6](#) and [Table 7](#); protocol Section 5.1).

Table 6: Dispensing Drug Kits based on Weight Group at Baseline/Day 1 Titration Scheme – Non-Impaired CYP2D6 Metabolizers

Weight Group	12 kg to <17 kg		17 kg to <30 kg		30 kg to <40 kg		≥40 kg	
Study Time Period	Dose (mg/day)	Tablets (mg)	Dose (mg/day)	Tablets (mg)	Dose (mg/day)	Tablets (mg)	Dose (mg/day)	Tablets (mg)
Day 2	6	6	6	6	6	6	6	6
Week 1	6	6	6	6	6	6	12	6, 6
Week 2	6	6	12	6, 6	12	6, 6	18	9, 9
Week 3	12	6, 6	18	9, 9	18	9, 9	24	12, 12
Week 4	12	6, 6	18	9, 9	24	12, 12	30	15, 15
Week 5	18	9, 9	24	12, 12	30	15, 15	36	18, 18
Week 6	18	9, 9	24	12, 12	36	18, 18	42	15, 6 AM 15, 6 PM
Week 7	24	12, 12	30	15, 15	42	15, 6 AM 15, 6 PM	48	12, 12 AM 12, 12 PM

CYP2D6=cytochrome P450 2D6. Dose and tables refer to IMP. Maximal dose according to the titration scheme is presented.

Table 7: Dispensing Drug Kits based on Weight Group at Baseline/Day 1 Titration Scheme – Impaired CYP2D6 Metabolizers

Weight Group	12 kg to <17 kg		17 kg to <30 kg		30 kg to <40 kg		≥40 kg	
Study Time Period	Dose (mg/day)	Tablets (mg)	Dose (mg/day)	Tablets (mg)	Dose (mg/day)	Tablets (mg)	Dose (mg/day)	Tablets (mg)
Day 2	6	6	6	6	6	6	6	6
Week 1	6	6	6	6	6	6	12	6, 6
Week 2	6	6	12	6, 6	12	6, 6	18	9, 9
Week 3	12	6, 6	18	9, 9	18	9, 9	24	12, 12
Week 4	12	6, 6	18	9, 9	24	12, 12	30	15, 15
Week 5	12	6, 6	18	9, 9	24	12, 12	36	18, 18
Week 6	12	6, 6	18	9, 9	24	12, 12	36	9, 9 AM 9, 9 PM
Week 7	12	6, 6	18	9, 9	24	6, 6 AM 6, 6 PM	36	9, 9 AM 9, 9 PM

CYP2D6=cytochrome P450 2D6. Dose and tables refer to IMP. Maximal dose according to the titration scheme is presented.

The number of tablets used is the number of tablets dispensed minus the number of tablets returned. If a patient does not return a pill bottle, it will be assumed that the patient took no IMP from that bottle for the purposes of calculating compliance.

The denominator of “expected number of tablets” will be calculated based on patients’ participation in the study (ie, last day of study drug – first day of study drug + 1) and the

expected dose according to the Randomization Trial Supply Management system. Adjustments may be required for the doses split between the morning and the evening dose. Of note, the protocol allows the investigator not to titrate a patient up to the maximal possible dose by weight group and CYP2D6 impairment status; therefore the expected number of tablets will be calculated individually. Moreover, drug suspensions and reductions based on investigator instructions are considered as change in the expected number of tablets and are not considered non-compliance. For patients who complete the study, the last day of study drug used in the denominator calculation will be the last expected dosing day. For early termination patients, the last day of study drug used in the denominator calculation will be the last expected dosing day before termination day.

A patient will be deemed compliant over the treatment period if the patient has taken 80% to 105% of the expected tablets of study drug.

Treatment compliance (%) will be summarized as continuous data using descriptive statistics. In addition, treatment compliance will be summarized as categorical data using descriptive statistics for the following categories: <80%, 80% to 105%, >105%. Compliance will be presented by visit, by overall in the titration and maintenance periods, and by overall in the treatment period.

An additional assessment of the IMP compliance may be performed while taking into account the patient's dose.

5.9. Study Protocol Deviations

Any protocol deviation (as recorded in the Clinical Trial Management System [CTMS]) that affects, to a significant degree, (a) the safety, physical, or mental integrity of the patients in the study and/or (b) the scientific value of the study will be considered an important protocol deviation.

Important protocol deviation will be summarized overall and for each category using descriptive statistics. All protocol deviations will be listed.

6. EFFICACY ANALYSIS

6.1. General

The ITT analysis sets will be used for all efficacy analyses. All efficacy endpoints will be summarized using descriptive statistics.

6.2. Efficacy Endpoints and Analysis

Descriptive statistics for continuous variables include n, mean, SD, SE of the mean, median, minimum, and maximum. Minimum and maximum will have the same number of decimal points as the original data. Mean and median will have 1 more decimal point than the original data. SD and SE will have 2 more decimal points than the original data.

Note, descriptive statistics of change from baseline will utilize day 1 from the present open-label study (Study TEV-50717-30081) or week 16 visit from the parent double-blind study (Study TV50717-CNS-30080).

6.2.1. Efficacy Endpoints

Efficacy endpoints will be assessed in this study as follows:

- MD-CRS part I total score (centrally read)
- MD-CRS part II total score (centrally read)
- MD-CRS part I total score (physician rated)
- MD-CRS part II total score (physician rated)
- MD-CRS Global Index (calculated from MD-CRS parts I and II total scores)
- Caregiver Global Impression of Improvement (CaGI-I) Scale (global, caregiver rated)
- Clinical Global Impression of Improvement (CGI-I) Scale (global, physician rated)
- Clinical Global Impression of Severity (CGI-S) Scale (global, physician rated)
- Pediatric Evaluation Disability Inventory-Computer Adapter Test (PEDI-CAT) (ADL, caregiver completed, content-balanced version)
- Unified Huntington's Disease Rating Scale-Total Maximal Chorea (UHDRS-TMC) (centrally read)
- Unified Huntington's Disease Rating Scale-Total Maximal Dystonia (UHDRS-TMD) (centrally read)
- Unified Huntington's Disease Rating Scale-Total Motor Score (UHDRS-TMS) (physician rated)
- UHDRS-TMC (physician rated)
- UHDRS-TMD (physician rated)
- Canadian Occupational Performance Measure (COPM) (physician rated)

6.2.2. Efficacy Analysis

6.2.2.1. Movement Disorder-Childhood Rating Scale

The MD-CRS includes 2 parts: part I for general assessment of the patient's functioning and impact of cerebral palsy on the activities of the patient and part II for a specific motor assessment of the severity of the movement disorder. All items are scored on a 5-point ordinal scale (0-4). Zero corresponds to no signs, and 4 corresponds to the most severe findings.

The MD-CRS Part I:

There are 15 items in MD-CRS part I to evaluate the impact of DCP on the activities of the patient and provides a general assessment of the movement disorder of motor function (7 items), oral/verbal function (3 items), self-care (3 items), and attention/alertness (2 items) on a scale of 0 (present) to 4 (absent). Items A1-A7 (Motor function), C1 (Self-dressing) and D1 (Attention/alertness during the observation) are scored by the rater in the clinic and these are video recorded for central reading, all other part I items are scored by the rater based on the parent/caregiver interview. Each item is on a 0 (present) to 4 (absent) scale. The minimum score is 0 and the maximum score is 60.

In case of any missing items, MD-CRS part I total score will be derived by calculating the MD-CRS I index below, and multiplying by the maximum score of 60.

Note that the centrally-read MD-CRS part I total score is obtained by summing the centrally-read items (9 items) and the items that are scored only by the rater in the clinic (6 items). The physician rated MD-CRS part I total score is obtained by summing all 15 items by the rater in the clinic.

MD-CRS Part II:

There are 7 items in MD-CRS part II to evaluate the severity of the movement disorder in a scale of 0 to 4 in 7 body regions. In rating the movement disorder of the body part, 0 refers to absence of a movement disorder and 4 refers to a situation where movement disorder is present during all of the tasks for the region examined and/or involves 3 or more of the other regions, making completion impossible. All items are scored by the rater in the clinic and are centrally read based on video recording. The minimum score is 0 (absent) and the maximum score is 28 (marked/prolonged).

In case of any missing items, MD-CRS part II total score will be derived by calculating the MD-CRS II index below, and multiplying by the maximum score of 28.

The MD-CRS Global Index:

The MD-CRS Global Index is a global measure of the MD-CRS that consolidates the information from parts I and II using the method of weighted means of the 2 normalized indexes obtained from each part. The minimum score is 0 and the maximum score is 1.

The standardized/normalized score for each item of MD-CRS parts I and II with value X is calculated using the formula

$$X_{st} = \frac{X - X_{min}}{X_{max} - X_{min}}$$

where X_{max} is the maximum value for the score, and X_{min} is the minimum value for the score, or 4 and 0 respectively.

The normalized index for the scale, MD-CRS parts I or II, Index I or II, is calculated as the mean value of X_{st} .

The MD-CRS Global Index is the weighted mean of the normalized indexes for MD-CRS parts I and II using the formula:

$$\text{Global Index} = \frac{n_I \times \text{Index}_I + n_{II} \times \text{Index}_{II}}{n_I + n_{II}}$$

where n_I and n_{II} are the numbers of items in MD-CRS parts I and II respectively.

The actual values and change from baseline for the MD-CRS Part I, Part II and Global Index scores will be summarized.

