## **Section 6 Assessments of Efficacy**

In the event of an emergency situation (eg, the COVID-19 pandemic), in case a patient cannot return to the clinic for the scheduled visits (eg, due to quarantine, isolation, patient's concern, or closure of the site clinic), remote assessment may be allowed for the following:

- via nonrecording live video for the Clinical Global Impression of Improvement [CGI-I] mandatory at week 3 and week 7, Clinical Global Impression of Severity [CGI-S], Movement Disorder-Childhood Rating Scale [MD-CRS] parts I and II, Unified Huntington's Disease Rating Scale-Total Motor Score [UHDRS-TMS], and the Canadian Occupational Performance Measure [COPM], as applicable. The results of the questionnaires will be entered to the case report form (CRF) per the usual process indicating that the rating has been performed remotely.
- via iPhone® (Apple, Inc) or via paper back-up copy instead of iPad® (Apple Inc) for the Caregiver Global Impression of Improvement [CaGI-I] and the Pediatric Evaluation Disability Inventory-Computer Adapted Test [PEDI-CAT], as applicable. The results of the questionnaires will be transferred to the CRF per the usual process (either from iPhone or from paper back-up copy).

The MD-CRS Part I & II are optional at the investigator's discretion and may be incomplete considering patient's imbalance when standing and walking and prioritizing patient safety. UHDRS-TMS should be completed as much as possible; some fields (ie, rigidity, stability) may be left blank as they cannot be assessed remotely. The pull test should not be done due to safety considerations.

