6.2.2.6. Unified Huntington's Disease Rating Scale-Total Motor Score

UHDRS-TMS comprises a broad assessment of features associated with Huntington's Disease. The TMS component of UHDRS comprises 31 assessments from the 15 items of the UHDRS. The TMS is calculated as the sum of the 31 motor assessments, each of which range between 0 to 4. The minimum score is 0 (absent) and the maximum score is 124 (worst).

UHDRS-TMC is part of the UHDRS-TMS assessment and assesses the severity of chorea in the face, mouth, trunk, and the 4 extremities. The minimum score is 0 (absent), and the maximum score is 28 (marked/prolonged).

UHDRS-TMD is part of the UHDRS-TMS assessment and assesses the severity of dystonia in the trunk and the 4 extremities. The minimum score is 0 (absent), and the maximum score is 20 (marked/prolonged).

If responses of up to 25% of items are missing in UHDRS-TMS, UHDRS-TMC, or UHDRS-TMD ("scale"), the missing responses will be replaced by the average of the remaining responses within each of the scales. If 8 or more of the items are missing, the missing items will not be replaced and the scale will be set to missing.

The actual values and change from baseline for the UHDRS-TMS, TMC and TMD will be summarized.

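### SAP 6.2.2.1 prorates MD-CRS totals with no minimum number of items, so an unread visit can yield a centrally read Part I total with no centrally read item; the UHDRS set-to-missing limit fits only the TMS

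*SAP*

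**What the plan says.** For a Part I total with gaps, SAP 6.2.2.1 says: "In case of any missing items, MD-CRS part I total score will be derived by calculating the MD-CRS I index below", with the result multiplied by 60. For Part II: "In case of any missing items, MD-CRS part II total score will be derived by calculating the MD-CRS II index below", multiplied by 28. The index is defined as follows: "The normalized index for the scale, MD-CRS parts I or II, Index I or II, is calculated as the mean value of" the standardised item scores, each item being divided by 4. No minimum number of observed items is given. SAP 4.3 places the missing-item rules for rating scales in SAP 6.2.2 and Section 8, and neither adds an MD-CRS minimum.

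The same section names nine Part I items that are recorded for central reading: the seven motor items A1–A7, self-dressing (C1) and observed attention (D1). Of the rest it says: "all other part I items are scored by the rater based on the parent/caregiver interview". The centrally read Part I total is obtained by "summing the centrally-read items (9 items) and the items that are scored only by the rater in the clinic (6 items").

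For the UHDRS scales, SAP 6.2.2.6 has two sentences. The first is a replacement cap: "If responses of up to 25% of items are missing in UHDRS-TMS, UHDRS-TMC, or UHDRS-TMD", the gaps are filled with the average of the responses present on that scale. The second is a set-to-missing limit: "If 8 or more of the items are missing, the missing items will not be replaced and the scale will be set to missing".

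Protocol Appendix M (Section 6) allows remote assessment "via nonrecording live video for the Clinical Global Impression of Improvement" and, in the same list, for MD-CRS Parts I and II. It adds that a remote MD-CRS is optional and may be incomplete. A footnote to SAP Table 3 says that central reading works from the video recordings.

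**The concern.** The centrally read and physician-rated Part I totals are separate efficacy endpoints (SAP 6.2.1). When there is no recording, the nine video items go missing as a block, and all seven motor items go with them. A rule that prorates for any gap, however large, then produces a number from the six interview items and files it under the centrally read endpoint. If one visit was read and another was not, the change from day 1 compares a score dominated by observed motor function with one that contains none.

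Elsewhere the SAP usually does set a limit: no missing item for the ESS, one item for two CBCL Competence subscales, 20 items for the CBCL Syndrome Scale and 25% for the UHDRS. On the UHDRS, however, the second sentence gives one absolute count for three scales of very different length, so programmers have no instruction for the two short ones.

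**Working it through.** **UHDRS: reproducing the figure of 8.** Item counts come from SAP 6.2.2.6. The TMS has 31 assessments, the TMC has 7 (face, mouth, trunk, four extremities) and the TMD has 5 (trunk, four extremities).

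- TMS: 0.25 × 31 = 7.75. Up to 7 missing items are replaced, and 8 or more set the scale to missing. The stated limit is reproduced exactly.
- TMC: 0.25 × 7 = 1.75. One missing item is replaced. From 2 missing the cap is exceeded, but 8 can never be reached on 7 items.
- TMD: 0.25 × 5 = 1.25. Again one item is replaced, and 8 can never be reached on 5 items.

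A TMC with 2–6 items missing, or a TMD with 2–4 missing, is therefore neither replaced nor set to missing. The SAP does not say whether the result is missing or a partial sum.

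The limit of 8 also depends on the SAP's count of 31. Protocol 6.1.6 gives a TMS maximum of 108. At 4 points per item that implies 108 / 4 = 27 assessments and 0.25 × 27 = 6.75, so a limit of 7.

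**MD-CRS Part I with no central read.** There are 15 items: 7 motor, 3 oral/verbal, 3 self-care and 2 attention. Nine are central (7 + 1 + 1), and the 6 interview items are 3 oral/verbal, 2 self-care and 1 attention. Let c and s be the mean raw scores (0–4) of the 9 central and 6 interview items.

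- Check with nothing missing and every item at 2: 60 × (2/4) = 30 = 15 × 2. The proration formula itself is sound.
- Full total: 9c + 6s.
- Total with the central block absent (9 of 15 items, 60%): 60 × (s/4) = 15s.
- Error: 15s − (9c + 6s) = 9 × (s − c).

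The error is zero when s = c. Because items run from 0 to 4, it cannot exceed 9 × 4 = 36 points either way. The documents give no item-level data. For assumed gaps between s and c of 0.25, 0.5 and 1.0 points, it would be 2.25, 4.5 and 9 points, sign unknown.

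An assumed example for change: c falls from 3 to 1 and s stays at 2. The full totals are 27 + 12 = 39 and 9 + 12 = 21, a change of −18. If the later visit is unread, its total is 15 × 2 = 30 and the reported change is −9.

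**MD-CRS Part II.** With no central read there are no items, the mean is undefined and no total arises. With partial gaps, one observed item x gives 28 × (x/4) = 7x, so the total can only be 0, 7, 14, 21 or 28.

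**Where an unread visit can arise.** Central reading is planned at day 1 and weeks 27, 53/ET and 54 (Protocol 6.1.1). Appendix M (Section 3.5) has remote weeks 53 and 54 repeated in clinic with all assessments, so the documented route is mainly a remote week 27. That appendix also asks for an unscheduled site visit afterwards. But SAP 4.4 prefers a non-missing scheduled record to an unscheduled one. If the remote visit is stored as scheduled, its prorated six-item total could count as non-missing and displace a later visit that was recorded.

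**The case against.** The strongest reply is that a visit without a central read is a missing assessment, not an assessment with missing items. The centrally read total is defined as a sum that includes nine centrally read items, and SAP 4.3 generally uses observed data. The central reading charter mentioned in Protocol 6.1.1 is not among the documents and may settle this. The intent is plausible, but the SAP's words cover any missing items and do not exclude an absent read. The six-item total is therefore what the rule gives when read literally; it is not an established programming result.

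It is also fair to say that the UHDRS 25% cap works on all three scales, so nothing is wrongly imputed. No documented route to partial TMC or TMD gaps is shown, since the remote blanks that Appendix M names are rigidity and stability. What remains is an undefined outcome.

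Two stronger readings are tempting:

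- **Day 1.** Video recording was added by Amendment 03, so a reader might infer that patients enrolled before it have interview-only baselines, and might put a number on them. The documents do not support a count or a group shift. Protocol 6.1.6 says the central UHDRS rating covers all patients, using the MD-CRS videos. Same-day rollovers may use parent-study week 16 scales, whose recording status is not stated. Under Appendix D, sites might have begun recording only after local approval. Whether any early day 1 visit lacks a video is unknown.
- **ESRS.** A reader might infer that a remote ESRS II with rigidity and stability blank would have those items filled from the rest of the scale. SAP 8.14.1 and 8.14.2 take the replacement from the remaining responses inside the item. On that wording a wholly blank item has nothing to average. The rule is ambiguous, and no share of imputed items should be quoted.

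**Conclusion.** The point holds as a minor drafting defect in two stated rules. SAP 6.2.2.1 has no minimum for prorating and, taken literally, allows a centrally read Part I total with no centrally read item and no motor item. The error per affected visit is 9 × (s − c) points. The number of affected visits, the sign and the actual size cannot be obtained from the documents. This conclusion assumes that an absent read counts as missing items, which the SAP neither states nor rules out. In SAP 6.2.2.6 the limit of 8 is right for a 31-assessment TMS and has no effect on the TMC or TMD.

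The MD-CRS and UHDRS outputs are secondary and descriptive, so no test or error rate is affected.

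**What to change.** - **SAP 6.2.2.1:** state that the centrally read Part I total is missing when the central read is absent. Set a minimum before prorating either part. The SAP's own 25% limit is one option: at most 3 of 15 items missing for Part I (0.25 × 15 = 3.75) and 1 of 7 for Part II (0.25 × 7 = 1.75). This also stops an unread remote record from displacing a later recorded one under SAP 4.4.
- **SAP 6.2.2.6:** replace the absolute count of 8 with more than 25% of the items of the scale concerned. That gives 8 or more for the TMS on 31 assessments and 2 or more for the TMC and TMD. It also remains correct if the TMS item count is reconciled with the protocol's maximum of 108.
- **SAP 8.14.1 and 8.14.2:** clarify what the ESRS replacement averages over, and how a remote visit with rigidity and stability blank (Appendix M, Section 7.2) is scored.

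The cost is a few sentences and some programming before database lock, and a few scores that become missing instead of being built from too few items.
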